4.2.7.5 Sensitivity analyses

Sensitivity analyses for the primary and key secondary endpoints will be used to explore the robustness of any treatment effect, if the amount of missing data warrants further investigation.

Alternative estimand approaches for handling intercurrent events will be explored including treatment policy approaches, or alternative imputation techniques for handling of treatment failure intercurrent events for continuous endpoints, if relevant.

For missing data due to study withdrawal or incomplete data for other reasons, different missing data mechanisms (eg, values missing at random [MAR] and values missing not at random [MNAR]) will be considered to assess the robustness of the treatment effect for these endpoints. The use of multiple imputation approaches, including dropout reason-based multiple imputation will be considered.

To examine the impact of missing data, including the impact of non-responder/not relapse free imputations due to study withdrawal, for the primary and first key secondary endpoint respectively, tipping point analyses may be performed. These analyses will systematically vary the assumptions about outcomes among the subsets of participants on the treatment arms who withdraw from the study early or have missing data at Week 36 for any other reason. Tipping point analyses are intended to identify the point at which the results would tip from statistically significant to not statistically significant. Thus, the tipping point analyses will only be performed if an endpoint achieves a nominally statistically significant result (ie, nominal p-value < 0.05).

Details using multiple imputation techniques are specified in Appendix [8.1](#).

To explore the primary analysis estimand approach, a sensitivity analysis may be performed whereby an increase in OCS dose after previously achieving disease control will be considered an intercurrent event, and the participant being considered a non-responder in the analysis.

4.2.8 Secondary efficacy outcome variables

4.2.8.1 Proportion of participants in sustained complete/partial remission on minimal OCS/off OCS for at least 2 months at Week 36

More details on derivation rules and intercurrent events are given in Section [3.4.1](#).

The statistical methodology described for the primary analysis will be carried out for this endpoint.

The p-value will be nominal, as secondary objectives are not controlled for multiplicity and do not appear in the testing hierarchy.

Summaries of the different combinations of complete and partial remission, each on minimal OCS or off OCS, will also be produced to understand the distribution of these clinical benefit categories at visits throughout the study up to Week 36.

4.2.8.2 Cumulative time (weeks) in complete remission off OCS from baseline to Week 36

Cumulative time in complete remission while off OCS will be derived for each participant over the initial 36-week treatment period. More details on derivation rules and intercurrent events are given in Section [3.4.2](#).

Cumulative time in complete remission while off OCS will be categorized as per Section [3.4.2](#).

An ordered logistics regression model will be fitted to these categories, assuming proportional odds. The model will include cumulative time as the dependent variable and treatment, baseline disease severity and time of BP diagnosis as categorical covariates. The model will be used to estimate an odds ratio, with 95% CIs.

The p-value will be nominal, as secondary objectives are not controlled for multiplicity and do not appear in the testing hierarchy.

Cumulative time (weeks) in complete or partial remission off OCS from baseline to Week 36 will be also analysed in an exploratory way using same methodology.

4.2.8.3 Proportion of participants off OCS by Week 36

Participants will be defined as responders if they are off OCS by Week 36. Otherwise, participants will be classified as non-responders. More details on derivation rules and intercurrent events are given in Section [3.4.3](#).

The statistical methodology described for the primary analysis will be carried out for this endpoint.

The p-value will be nominal, as secondary objectives are not controlled for multiplicity and do not appear in the testing hierarchy.

To support this analysis, the observed proportion of responders will be summarized using descriptive statistics by treatment group and each scheduled visit up to Week 36.

4.2.8.4 IGA score at Week 36 and change from baseline in IGA score at Week 36

IGA score achieved (clear, almost clear, mild, moderate, severe) will be summarized using descriptive statistics by treatment group at each scheduled visit up to Week 36.

A responder analysis will be performed where participants will be classified as responders if they achieve IGA 0/1 (ie, clear or almost clear) at Week 36. Otherwise, participants will be classified as non-responders. The statistical methodology described for the primary analysis will be carried out for this endpoint (the p-value will be nominal, as secondary objectives are not controlled for multiplicity and do not appear in the testing hierarchy).

Number of points change from baseline in IGA score will be summarized, and a shift table comparing IGA score at baseline against IGA score achieved at Week 36 (and other visits throughout the study, as relevant) will be produced.

4.2.8.5 Proportion of participants who remain relapse-free up to Week 16

Referring to the statistical analysis for the proportion of participants who remain relapse-free up to Week 36, the proportion of participants who remain relapse-free up to Week 16 will be analyzed as a binary endpoint with a logistic regression model similar to the one applied to the analysis at Week 36.

4.2.8.6 Proportion of participants with any clinical benefit at Week 16

To assess signs of clinical efficacy during the first 16 weeks of the study, the observed proportion of participants showing partial remission or complete remission at Week 16 will be summarized using descriptive statistics by treatment group. Results will be also presented within OCS usage as reported in Section [3.4.6](#).

If a consistent message can be drawn across these categories and treatment groups, a supportive analysis will be carried out, whereby a participant will be classified as a responder if they show any clinical benefit (ie, partial remission or complete remission) during taper, with no steroids or with minimal steroid use at Week 16. Otherwise, a participant will be classified as a non-responder.

This binary variable will then be analysed using a logistic regression model and applying the same statistical methodology as described for the primary analysis in Section [4.2.6.1](#).

The p-value will be nominal, as secondary objectives are not controlled for multiplicity and do not appear in the testing hierarchy.

4.2.8.7 Time to disease control, OCS dose at disease control and time to the end of the consolidation phase

Time to disease control, OCS dose at disease control and time to the end of the consolidation phase will be summarized using descriptive statistics by treatment group.

Statistical analyses and Kaplan Meier plots may be performed if appropriate.

4.2.8.8 Change from baseline in BPDAI activity score at Week 16

Referring to the statistical analysis for change from baseline in BPDAI activity score at Week 36, the same analysis method will be used for the change from baseline at Week 16 endpoint.

The p-value at Week 16 will be nominal, as secondary objectives are not controlled for multiplicity and do not appear in the testing hierarchy.

4.2.8.9 Change from baseline in BPDAI-Pruritus score at Week 16

Referring to the statistical analysis for change from baseline in BPDAI-Pruritus score at Week 36, the same analysis method will be used to provide an estimate at Week 16.

The p-value at Week 16 will be nominal, as secondary objectives are not controlled for multiplicity and do not appear in the testing hierarchy.

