### **Proportion of participants with any clinical benefit at Week 16**

To assess signs of clinical efficacy during the first 16 weeks of the study, the observed proportion of participants showing partial remission or complete remission at Week 16 will be summarized using descriptive statistics by treatment group. The summary will categorize each of these disease states into: during taper, with no steroids, and with minimal steroids (ie, < 0.1 mg/kg/day).

If a consistent message can be drawn across these categories and treatment groups, a supportive analysis will be carried out, whereby a participant will be classified as a responder if they show any clinical benefit (ie, partial remission or complete remission) during taper, with no steroids or with minimal steroid use at Week 16. Otherwise, a participant will be classified as a non-responder. This binary variable will then be analyzed using a logistic regression model with a logit link function. The model will include treatment, baseline disease severity and time of BP diagnosis as covariates. The model will be used to estimate the proportion of responders for benralizumab and placebo, the difference between these proportions (benralizumab – placebo) and an odds ratio, with corresponding 95% confidence limits. A p-value, corresponding to a 2-sided test, will be presented to compare the benralizumab and placebo treatment groups. (The p-value will be nominal, as secondary objectives are not controlled for multiplicity and do not appear in the testing hierarchy.)

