1.1 Study objectives

Table 1 Objectives and Endpoints

Objective	Estimand descriptions/Endpoints
Primary	
To compare the clinical efficacy of benralizumab with placebo in participants with symptomatic BP	
Population: Full analysis set.Endpoint: A binary response, whereby a responder is defined as a participant who is in complete remission while off OCS for ≥ 2 months at Week 36. Otherwise, a participant is a non-responder.Intercurrent events: Participants who receive restricted medications or withdraw from the study will be considered as non-responders from the time such events occur up to Week 36.Summary measure: Difference in proportion of participants who are responders between benralizumab and placebo at Week 36.
Secondary	
To compare the effect of benralizumab with placebo on supportive measures of clinical efficacy in participants with symptomatic BP up to Week 36	
Key secondary ^a: Proportion of participants who remain relapse-free up to Week 36.Key secondary ^a: Cumulative OCS exposure (mg/kg) from baseline to Week 36.Key secondary ^a: Change from baseline in BPDAI activity score at Week 36.Key secondary ^a: Change from baseline in BPDAI-Pruritus score at Week 36.Proportion of participants in sustained complete/partial remission on minimal OCS/off OCS for at least 2 months at Week 36.Cumulative time (weeks) in complete remission off OCS from baseline to Week 36.Proportion of participants off OCS by Week 36.IGA score at Week 36.Change from baseline in IGA score at Week 36.

Table 1 Objectives and Endpoints

Objective	Estimand descriptions/Endpoints
To compare the effect of benralizumab with placebo on clinical efficacy in participants with symptomatic BP up to Week 16	
 Key secondary^a Cumulative OCS exposure (mg/kg) from baseline to Week 16. Proportion of participants who remain relapse-free up to Week 16. Proportion of participants with any clinical benefit (eg, partial and complete remission during taper, with no steroid use, or with minimal steroid use [ie, < 0.1 mg/kg/day]) at Week 16. Time to disease control, OCS dose (mg/kg) at disease control and time to the end of the consolidation phase. Change from baseline in BPDAI activity score at Week 16. Change from baseline in BPDAI-Pruritus score at Week 16.

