- Participants who need to increase their OCS dose as a rescue therapy to treat their BP after having previously achieved disease control will have their last observed value prior to the date of OCS dose increase recorded with start date > date of disease control assessment carried forward to subsequent visits. If baseline is the last available assessment prior to the date of OCS dose increase, then it will be used to impute the missing data.
- For participants who withdraw from the study without having rescue or restricted medications, missing values will remain missing. The same approach will be applied to those participants with missing data for any other reason.

A responder analysis will be performed where participants will be classified as responders if they achieve IGA 0/1 (ie, clear or almost clear) at Week 36. Otherwise, participants will be classified as non-responders.

The same derivation rules and the same intercurrent events as described for the primary analysis will be applied whereby patients with the intercurrent events will be considered as non responders in the analysis.

3.4.5 Proportion of participants who remain relapse-free up to Week 16

The same derivation rules and the same intercurrent events described for the key secondary analysis on the proportion of participants who remain relapse-free up to Week 36 will be applied for the analysis of the proportion of participants who remain relapse-free up to Week 16.

3.4.6 Proportion of participants with any clinical benefit at Week 16

Participants will be defined as responders if they are in partial remission or complete remission at Week 16 as assessed by Investigator. Otherwise, participants will be classified as non-responders.

Responders will be further categorized based on their disease status and OCS data into:

- Partial remission
 - On minimal steroid (less than or equal to 0.1 mg/kg/day of OCS)
 - Off steroid therapy
- Complete remission
 - On minimal steroid (less than or equal to 0.1 mg/kg/day of OCS)
 - Off steroid therapy

3.4.7 Time to disease control, OCS dose at disease control and time to the end of the consolidation phase

As detailed in Section 3.2, Investigators will be asked to make a clinical assessment of the participants to determine their BP disease state.

Disease control is achieved at the time when new lesions cease to form, and established lesions begin to heal, or pruritic symptoms start to abate.

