4 ANALYSIS METHODS

4.1 General principles

The primary analysis will be based on the initial 36-week, double-blind, placebo-controlled phase of the study, and will compare all participants randomized to benralizumab until Week 36 against all participants randomized to placebo until Week 36.

All personnel involved in the analyses of the study will remain blinded until the primary DBL and protocol deviations are identified.

The current SAP focuses on the double-blind study period with a high-level description of the descriptive analysis for the OLE analysis. If required, additional detail regarding descriptive analyses in the OLE period will be provided in a separate OLE SAP.

The primary CSR will focus on data from the double-blind period as defined in Section [3.1.2](#).
Final data collected during the OLE period will be reported separately.

Efficacy endpoints will be analysed using the FAS, the analysis of safety endpoints will be based on the safety analysis set. Analysis sets are defined in Section [2.1](#).

Summary data will be presented in tabular format by treatment group. Categorical data will be summarized using frequency and percentages, where the denominator for calculation is the underlying analysis set population unless otherwise stated. Continuous data will be summarized with descriptive statistics of number of available observations, mean, standard deviation, median, minimum and maximum, and quartiles where more appropriate. Data listings will be sorted by treatment and participant number.

All point estimates will be presented together with 95% confidence intervals (CIs) as measures of precision and nominal 2-sided p-values, rounded to 4 decimal places.

Hypothesis testing for the primary and key secondary endpoints will be based on a 2-sided test and carried out using a 5% significance level. If a p-value is less than 0.05, the treatment effect favours benralizumab and the decision will be to reject the null hypothesis (H0) and the alternative hypothesis (H1) will be accepted, subject to the testing strategy outlined in Section [4.1.1](#) below. Any p-values presented for endpoints other than those included in the testing strategy will be nominal (i.e. not multiplicity adjusted).

All analyses for the OLE endpoints will be descriptive, as no placebo-control data will be available for this period. Consequently, no hypothesis testing will be performed.

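### The Week 16 any-clinical-benefit model is fitted only if an undefined consistency condition is met on the unblinded results, so its reporting depends on the result (minor)

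*SAP*

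**What the plan says.** The endpoint is a listed secondary, though not a key secondary, in SAP 1.1 Table 1: "Proportion of participants with any clinical benefit (eg, partial and complete remission during taper, with no steroid use, or with minimal steroid use" at Week 16. It sits under an objective to compare benralizumab with placebo up to Week 16.

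SAP 4.2.8.6 has two layers.

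- **Unconditional.** It says that "the observed proportion of participants showing partial remission or complete remission at Week 16 will be summarized using descriptive statistics by treatment group", with a further presentation by OCS use.
- **Conditional.** "If a consistent message can be drawn across these categories and treatment groups, a supportive analysis will be carried out". If the condition is met, "This binary variable will then be analysed using a logistic regression model and applying the same statistical methodology as described for the primary analysis", which brings an odds ratio, an adjusted difference, confidence intervals and a p-value.

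Protocol 9.4.2.3 states the same condition in the same words. Neither document says what counts as consistent, who decides, or when. On the status of the result, the SAP's wording for secondary endpoints, which 4.2.8.6 also carries, is that "the p-value will be nominal, as secondary objectives are not controlled for multiplicity and do not appear in the testing hierarchy".

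The categories to be judged are not settled either. For the protocol, "The summary will categorize each of these disease states into: during taper, with no steroids, and with minimal steroids", which over partial and complete remission makes six cells. In SAP 3.4.6, "Responders will be further categorized based on their disease status and OCS data into" introduces four cells (partial or complete remission, each on minimal OCS or off OCS), with no taper category. SAP 4.2.8.6 nevertheless keeps taper in the responder definition.

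**The concern.** The condition refers to treatment groups, and SAP 4.1 keeps analysis personnel blinded until the primary database lock. The judgement is therefore made on the unblinded comparison that the model would then test. The rule decides, from the result, whether the endpoint's only model-based comparison is produced.

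A p-value that is seen only when its components line up does not have a 5% error rate among the occasions on which it is seen, and its confidence interval does not have 95% coverage there. Labelling it nominal tells the reader that multiplicity is uncontrolled. It does not say that the result was selected on its own data.

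The plan handles comparable choices more tightly elsewhere. The list of intercurrent-event medications (SAP 3.1.5.2), the cumulative-remission categories (3.4.2), the itch responder definition (3.6.1) and the dropout-reason review (8.1.3) must all be fixed before unblinding. The other secondary responder analyses and the Week 16 BPDAI analyses (4.2.8.1, 4.2.8.3 to 4.2.8.5, 4.2.8.8, 4.2.8.9) are unconditional. The time-to-disease-control endpoints in 4.2.8.7 are also left to discretion, but there the text only permits an analysis where appropriate and does not tie it to a pattern in the results.

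**Working it through.** **The plan's own figure.** The documents give no rate, power or sample size for this endpoint. The only related figure is 50 per group for 85% power at 50% versus 20% on the primary endpoint (SAP 1.3). The usual formula is n = [z(0.975)·√(2p̄q̄) + z(0.85)·√(p₁q₁+p₂q₂)]² / d², with p̄ = 0.35 and d = 0.30:

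[1.960 × √0.455 + 1.036 × √0.41]² / 0.09 ≈ 44 per group, or 51 with continuity correction.

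The stated 50 therefore reproduces to within one participant on the corrected version. Only the 50 per arm is used below.

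**Inputs for the illustration.**

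- From the documents: 50 per arm, 1:1 allocation, four cells (SAP 3.4.6) or six (Protocol 9.4.2.3). The nominal level is 5%, 2-sided; SAP 4.1 states "based on a 2-sided test and carried out using a 5% significance level" for the primary and key secondary endpoints, and it is borrowed here.
- Assumed: the Week 16 benefit rate (20%, 40% or 60% in both arms, split equally over the cells) and the meaning of consistent.
- Method: multinomial simulation with no true difference, 400,000 trials per scenario. For four and six cells a pooled two-proportion z-test stands in for the logistic model. The two-category row (20% complete, 20% partial remission) uses a Wald test of the log odds ratio.

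The per-trial rate is P(model reported) × P(p<0.05 given reported).

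**Results at 40% benefit in both arms.**

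| Reading of the condition | Reported | p<0.05 if reported | Mean reported difference (points) | Per-trial rate |
|---|---|---|---|---|
| Always fitted | 100% | 5.3% | 0 | 5.3% |
| Overall proportion favours benralizumab | 45.9% | 5.8% | +8.5 | 0.459 × 0.058 = 2.7% |
| No category against benralizumab, 2 categories | 26% | 9.3% | +10 | 0.26 × 0.093 = 2.4% |
| Same, 4 cells | 6.9% | 21.9% | +14.1 | 0.069 × 0.219 = 1.5% |
| Same, 6 cells | 2.1% | 33.9% | +16.7 | 0.021 × 0.339 = 0.7% |
| All cells agree, either direction, 4 cells | 14.0% | 21.9% | about 0 | 0.140 × 0.219 = 3.1% |
| All cells agree, either direction, 6 cells | 4.2% | 34.3% | about 0 | 0.042 × 0.343 = 1.4% |

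Under the loose reading in the second row, all the 5.8% favour benralizumab, against 2.6% in that direction when the model is always fitted.

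**Sensitivity to the assumed rate (20% to 60%).** With no category against benralizumab, p<0.05 occurs in 18–25% of reported models with four cells and 28–40% with six. If all but one category must favour benralizumab, the figures are 13–14% and 36–43%. The loose reading stays at about 6%.

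**With a true effect.** At an assumed 55% versus 40% with four cells, the strict favourable rule reports the model in 31% of trials, with a mean difference of 22 points where the truth is 15. The condition can therefore also suppress a real effect.

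**The case against.** The strongest reply is that little depends on this model. The endpoint is not a key secondary, the analysis is called supportive, and its p-value is nominal and outside the six-step hierarchy. That stands, and it limits the severity.

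Four stronger readings are tempting, and the documents do not support them.

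- **That an unfavourable or mixed result would be hidden.** Proportions by arm are tabulated whatever happens, and SAP 4.2.8.1 also tabulates the remission-by-OCS combinations at visits up to Week 36. A reader can compute the crude difference. Only the model-based comparison can disappear.
- **That the trial's chance of a false positive rises.** The condition can only withhold a p-value, never create one, so the per-trial rate is at or below that of the unconditional model, as the last column shows. Only the rate conditional on reporting rises.
- **That the reported difference must be biased towards benralizumab.** The text names no direction. It could also be read as asking whether the categories are alike enough to pool. If agreement in either direction suffices, the conditional error rate is inflated but there is no mean bias.
- **That the p-value would be passed off as unconditional, or that the SAP departs from the protocol.** The condition is stated beforehand in identical words in both documents.

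It is also fair to say that the figures illustrate a mechanism and do not measure this plan. The conditional rate runs from about 6% to 43% across readings, because neither the criterion nor the Week 16 rates are given.

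**Conclusion.** The point holds as a minor one. An undefined condition, applied to results by treatment group, decides whether the only model-based odds ratio, adjusted difference, confidence interval and nominal p-value for a listed secondary endpoint are reported. Conditional on being reported, the p-value and interval do not have their stated error rate.

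The direction of that conclusion follows from the wording, but its size does not. Every figure rests on assumed Week 16 rates, an assumed meaning of consistent, and a simple two-group test in place of the covariate-adjusted model. Any bias in favour of benralizumab depends further on the condition being read in that direction. The primary and key secondary inference, the familywise error rate and the sample size are unaffected.

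**What to change.** Delete the condition in SAP 4.2.8.6 and replace it with a statement such as: the logistic regression of any clinical benefit at Week 16 will be carried out and reported whatever the descriptive breakdown shows. Keep the breakdown by remission type and OCS use as a descriptive table. List the change from Protocol 9.4.2.3 in SAP Section 6, since SAP Section 1 says that changes from the protocol are described there. The entry is needed only because of this edit, as the two documents now agree on the condition.

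The cost is one sentence of SAP text, one entry in Section 6 and one table that was already specified conditionally. No new data are needed. With the model always fitted, the nominal 2-sided error rate in the illustration returns to 5.2–5.3% with no mean bias.
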